4.1 Study Population

Participants 50 years of age or older with a fibromyalgia diagnosis that will be stratified by race/ethnicity; non-Hispanic Black, Hispanic, or non-Hispanic other (e.g., White, Asian).

4.2 Inclusion Criteria

1. Access to daily internet
2. Male or female 50 years of age or older
3. Fluent in English and able to read and write in English
4. Physician diagnosis of FMS AND/OR Score ≥ 13 on the 6-item, self-report fibromyalgia screening tool
5. Report having pain for at least the last three months

4.3 Exclusion Criteria

1. Cognitive impairment
2. Current behavioral treatment for pain
3. Enrolled in another pain study

4.4 Strategies for Recruitment and Retention

We will recruit fibromyalgia patients from offices at Weill Cornell Medicine/NewYork-Presbyterian (e.g., the Center on Aging (COA), the Cornell Internal Medicine Associates (CIMA), and the Iris Cantor Health Center). Co-PI [name], PI of the Cornell Roybal Center, has established a successful track record recruiting chronic pain patients for Roybal-supported research studies at Weill Cornell Medicine/NewYork-Presbyterian.

A total of 150 fibromyalgia patients will be recruited across Aims 1-2 once they have been identified by research and referring physicians confirmed to meet eligibility criteria. Based on prior recruitment at WCM/NYP we anticipate recruiting double the number of females than males, and will target enrollment to an equal number of non-Hispanic Black, Hispanic, or non-Hispanic other (e.g., White, Asian) equally between males and females. Participants will open-endedly self-report their race and ethnicity; the research team will ensure that the randomization process is stratified by Hispanic, non-Hispanic Black, and non-Hispanic other (e.g., White, Asian).

Normal patient participants will be recruited via physician-referred agree to contact sheets (paper or REDCap survey), flyers, and/or in-person recruitment. Physicians will utilize an Agree to Contact sheet that potential participants fill out with their contact information (phone, email, and/or mailing address) and sign agreeing to be contacted directly for the study by any of these methods.

Flyers will be distributed throughout WCM/NYP locations (including the Center on Aging), and distributed at senior centers, community centers, and community events. Additionally, co-investigators may approach potential participants in WCM/NYP offices (e.g. the Center on Aging), and ask if they would be interested in the study, when it is safe to do so under COVID-19 considerations. Trained co-investigators may either screen the participants at recruitment sites and/or ask for their contact information via the Agree to Contact sheet to be followed up at a time convenient for the potential participant.

Research staff will ask physicians at WCM/NYP, to review their patient lists and identify potential participants based on eligibility criteria both directly (e.g. email) and at department meetings. Research staff may also request EPIC provider reports based on eligibility requirements to reach out

to WCM/NYP physicians for permission to contact potential patient participants. Research staff will set EPIC search criteria to draw names from all networked EPIC databases accessible to Weill Cornell Medicine staff. Identified potential participants will be contacted via recruitment letter, email, or Weill/EPIC Connect. Recruitment letters may also be sent to potential participants via EPIC pool of WCM/NYP Consent to be Contacted for Research (CCR) patients and chart review to determine potential eligibility. Potential subjects will be sent a letter informing them of the study and that they will be contacted by a co-investigator who will assess interest in participating in the study. The letter will also provide a contact phone or email address that these patients can reach out to express their interest/disinterest for participation in the study.

Additional efforts will rely on making study information available on online platforms. Online platforms may include, but are not limited to: FMS interest pages on Facebook, participant registries, online bulletin boards, mobile apps and websites, etc. Methods include, but are not limited to: posting flyers, posting messages describing the project and inviting interested participants to contact study members (see "Social Media Posting" document), including study information in e-newsletters, etc. Permission from group administrators will be received prior to posting on any social media group platform. In addition, online research match databases including but not limited to ResearchMatch.org and the Institute for Translational Health Sciences will be added as a recruitment method.

Eligible participants will be compensated up to \$142 for completing the study. Participants will receive \$25 for each of the three study assessments (baseline, post-intervention, and 1-month follow up), up to \$42 (\$2 per survey) for the daily 5-10-minute surveys following the study assessments, and \$25 for the feedback survey. Activities completed during the 6-8 weeks of interaction on BrightOutcome will not be compensated.

Additionally, the following measures will be taken to improve retention. First, follow up emails, calls, or texts (depending on participant preference) to participants will be utilized to remind patients of upcoming study activity (online assessments, etc.). Text message reminders will be administered using the Twilio service, embedded via the CTSC in REDCap. Second, throughout the study period, accrual and retention rates will be monitored at weekly study meetings through reporting reasons for missed approaches, study refusal, and loss to follow up. This will allow the PI and study team members to notice quickly issues in accrual and/or retention and the potential reasons for it so that proper action can be taken to resolve the issue. Finally, all attempts have been made to keep assessments brief and flexible in order to reduce burden on the patients.

5. Registration Procedures

5.1 Subject Registration (WCM only)

Subjects will be registered within the WRG-CT as per the standard operating procedure for Subject Registration.

5.2 Subject Registration (Sub-sites)

Not applicable.

6. Study Procedures

6.1 Schedule of Assessments

Table 2. Schedule of trial events

Table 2: Type and Timing of Measures	PS	B	DS	PI	M1
Screening					
Age ≥ 50, read and understand English, FMS diagnosis, 6-item self-report FMS screening tool, cognitive functioning, no other behavioral treatment for pain, internet access, race/ethnicity	•				
Demographic and Clinical Characteristics					
Age, race/ethnicity, sex, income, education, employment, marital status Charlson Comorbidity Index		• •			
Pain					
Standardized Pain Measures Daily report of pain and fatigue		• •	•	• •	
Physical Function					
Body Mass Index (BMI) PROMIS Physical Function Short Form 10a PROMIS Fatigue Short Form 6a Exercise in the last 24 hrs		• • • •		• • • •	
Psychosocial Factors					
Standardized Psychosocial Factor Measures Daily stressors (DISE) Daily positive and negative affect Daily positive events		• • •	•	• •	
Feedback and Care Updates					
Feedback Survey Self-Enrolled Therapy Update				• •	

PS = pre-study; B = baseline; DS = daily survey; PI = post-intervention; M1 = 1-month follow-up

7. Data Reporting / Regulatory Considerations

7.1 Data Collection

The data collection plan for this study is to utilize REDCap to capture all data for all enrolled subjects.

7.1.1 REDCap

REDCap (Research Electronic Data Capture) is a free data management software system that is fully supported by the Weill-Cornell Medical Center CTSC. It is a tool for the creation of customized, secure data management systems that include Web-based data-entry forms, reporting tools, and a full array of security features including user and group-based privileges, authentication using institution LDAP system, with a full audit trail of data manipulation and export procedures. REDCap is maintained on CTSC-owned servers that are backed up nightly and support encrypted (SSL-based) connections. Nationally, the software is developed, enhanced and supported through a multi-institutional consortium led by the Vanderbilt University CTSA.

7.2 Regulatory Considerations

7.2.1 Institutional Review Board/Ethics Committee Approval

As required by local regulations, the Investigator will ensure all legal aspects are covered, and approval of the appropriate regulatory bodies obtained, before study initiation.

Before initiation of the study at each study center, the protocol, the ICF, other written material given to the patients, and any other relevant study documentation will be submitted to the appropriate Ethics Committee. Written approval of the study and all relevant study information must be obtained before the study center can be initiated or the IP is released to the Investigator. Any necessary extensions or renewals of IEC/IRB approval must be obtained for changes to the study, such as amendments to the protocol, the ICF, or other study documentation. The written approval of the IEC/IRB together with the approved ICF must be filed in the study files.

The Investigator will report promptly to the IEC/IRB any new information that may adversely affect the safety of the subjects or the conduct of the study. The Investigator will submit written summaries of the study status to the IEC/IRB as required. On completion of the study, the IEC/IRB will be notified that the study has ended.

All agreed protocol amendments will be clearly recorded on a protocol amendment form and will be signed and dated by the original protocol approving signatories. All protocol amendments will be submitted to the relevant institutional IEC/IRB for approval before implementation, as required by local regulations. The only exception will be when the amendment is necessary to eliminate an immediate hazard to the trial participants. In this case, the necessary action will be taken first, with the relevant protocol amendment following shortly thereafter.

Once protocol amendments or consent form modifications are implemented at the lead site, Weill Cornell Medicine, updated documents will be provided to participating sites. Weill Cornell Medicine must approve all consent form changes prior to local IRB submission.

Relevant study documentation will be submitted to the regulatory authorities of the participating countries, according to local/national requirements, for review and approval before the beginning of the study. On completion of the study, the regulatory authorities will be notified that the study has ended.

7.2.2 Ethical Conduct of the Study

The Investigators and all parties involved should conduct this study in adherence to the ethical principles based on the Declaration of Helsinki, GCP, ICH guidelines and the applicable national and local laws and regulatory requirements.

This study will be conducted under a protocol reviewed and approved by the applicable ethics committees and investigations will be undertaken by scientifically and medically qualified persons, where the benefits of the study are in proportion to the risks.

7.2.3 Informed Consent

The investigator or qualified designee must obtain documented consent according to ICH-GCP and local regulations, as applicable, from each potential subject or each subject's legally authorized representative prior to participating in the research study. Subjects who agree to participate will receive an oral consent document prior to speaking to a co-investigator.

Informed Consent and HIPAA authorization for participants will occur just prior to their baseline interview, by oral consent for participants until virtual consent methods are approved by the WCM IRB. For oral consent, a member of the study team will review the ICF and HIPAA Authorization document in-full (see *Oral Consent Script* attachment) by phone or videoconference, allowing for questions and reminding the potential subject that participation is voluntary. The subject and researcher will each recite their statements. Upon completion, oral confirmation of consent to participate will be documented by the study team member.

Once virtual consent processes are established with the JCTO, we will submit an amendment with the IRB to conform to these new policies. We feel that with our older adult population, at a higher risk to COVID-19, that this is best practices in human subjects for participants not to leave their home in order to participate in this study.

The initial ICF, any subsequent revised written ICF and any written information provided to the subject must approved by IRB prior to use. The ICF will adhere to IRB/IEC requirements, applicable laws and regulations.

7.2.4 Compliance with Trial Registration and Results Posting Requirements

Under the terms of the Food and Drug Administration Modernization Act (FDAMA) and the Food and Drug Administration Amendments Act (FDAAA), the Sponsor-Investigator of the trial is solely responsible for determining whether the trial and its results are subject to the requirements for submission to <http://www.clinicaltrials.gov>. Information posted will allow subjects to identify potentially appropriate trials for their disease conditions and pursue participation by calling a central contact number for further information on appropriate trial locations and trial site contact information.

7.2.5 Record Retention

Essential documents are those documents that individually and collectively permit evaluation of the study and quality of the data produced. After completion of the study, all documents and data relating to the study will be kept in an orderly manner by the Investigator in a secure study file. Essential documents should be retained for 2 years after the final marketing approval in an ICH region or for at least 2 years since the discontinuation of clinical development of the IP. In addition, all subject medical records and other source documentation will be kept for the maximum time permitted by the hospital, institution, or medical practice.

8. Statistical Considerations

Aim 1. Feasibility and acceptability will be examined by conducting frequency and descriptive statistics (i.e., mean, median, standard deviation, range) for enrollment rates, number of sessions completed, number of weeks required to complete the intervention, and Likert-scale items assessing satisfaction with the intervention and perceived helpfulness. **Aim 2.** Aim 2 will be addressed using a pre-post design. To determine the degree to which the LARKSPUR intervention is likely to improve patient outcomes, a post-versus-pre- difference will be sought to estimate the change in patients' outcomes (e.g., pain self-management). This is a small feasibility trial to explore the acceptability and feasibility of the intervention among racially and ethnically diverse older adults with fibromyalgia. The trial is not powered to estimate statistically reliable differences in outcomes. **Missing data.** All missing data will be assessed for missingness (e.g., random or non-random) and appropriate imputation methods will be used.

### 3 Abbreviations and Definitions

AE	Adverse Event
CRF	Case Report Form
CTSC	Clinical Translational Science Center
FMS	Fibromyalgia Syndrome
LARKSPUR	Lessons in Affect Regulation to Keep Stress and Pain Under control
PA	Positive Affect
SAP	Statistical Analysis Plan
REDCap	Research Electronic Data Capture

### 4 Introduction

#### 4.1 Preface

Chronic non-cancer pain affects as many as 100 million Americans and is associated with significant functional limitations and physical disability. Standard behavioral therapies typically focus on minimizing negative thoughts and emotions associated with pain and yield only modest treatment effects. Efforts are therefore needed to develop more effective

psychological treatments for chronic pain by identifying new targets for intervention. We propose to pilot test a resilience-based intervention that targets positive affect (PA) in fibromyalgia syndrome (FMS) patients, a chronic pain population with known deficits in PA and an inability to regulate PA in the face of pain. Our goal is to conduct a randomized pilot trial of LARKSPUR (Lessons in Affect Regulation to Keep Stress and Pain UndeR control), an online-delivered PA skills intervention. Our central hypothesis is that our LARKSPUR program will (a) show acceptability and feasibility in engaging and retaining FMS patients and (b) demonstrate greater improvements in PA and FMS-related pain and functional impairment.

This proposal for pilot data collection will lay the foundation for a high-quality randomized trial for people with FMS. The proposed work holds promise as an effective, low cost, scalable, and readily implementable novel non-pharmacologic intervention to help people cope with FMS. By demonstrating the feasibility, acceptability, and preliminary efficacy of the LARKSPUR intervention, we hope to improve quality of life, as well as the options available for care for millions of people who suffer from FMS.

#### **4.2 Scope of the analyses**

**Aim 1.** Feasibility and acceptability will be examined by conducting frequency and descriptive statistics (i.e., mean, median, standard deviation, range) for enrollment rates, number of sessions completed, number of weeks required to complete the intervention, and Likert-scale items assessing satisfaction with the intervention and perceived helpfulness.

**Aim 2.** Aim 2 will be addressed using a pre-post design. To determine the degree to which the LARKSPUR intervention is likely to improve patient outcomes, a post-versus-pre-difference will be sought to estimate the change in patients' outcomes (e.g., pain self-management). This is a small feasibility trial to explore the acceptability and feasibility of the intervention among racially and ethnically diverse older adults with fibromyalgia. The trial is not powered to estimate statistically reliable differences in outcomes.

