with basic skills for recognizing and savoring positive events and progressing to more complex skills such as goal-setting and acts of kindness.

A week will consist of 1-2 days of didactic material and 5-6 days of real-life skills practice and reporting. Participants cannot skip ahead and can only progress to the next lesson if they have completed the current one, but they can return to old lessons or exercises if they choose. As part of the daily home practice, intervention participants will be asked to complete the daily emotion check-in that comprises the attention control condition (which takes about 5 minutes to complete). Based on past studies, we estimate the time to read through a skill to be about 15 minutes per skill. We also encourage daily interaction with the website (home practice, reporting emotions) and estimate the time involved to be an additional about 10 minutes. Both the LARKSPUR intervention and emotion-reporting attention control conditions, including all home practice and assessments, will be done over the internet from the participant's home, or any other location of their choice. The intervention content, emotion check-in, and are all mobile-enabled so can be completed on desktop, laptop, tablet, or smartphone with web browser access.

Attention Control Condition (n = 75). We sought an attention control condition that provided something to engage participants, but was not expensive or burdensome. In past research we have established that emotion reporting is acceptable as an attention control condition (retention rates of ~80%, similar to or higher than for the intervention), and that participants perceive it as being beneficial, providing some of the features of a placebo control. In this daily emotion-reporting attention control condition, participants will be asked to report how they are feeling daily for 6-8 weeks which will be emailed to control participants.

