##### **5.1.1 Objective**

**5.1.1.1** To maximize relevance and acceptability of content and delivery of LARKSPUR intervention among patients with FMS, a chronic pain population with known deficits in PA. This aim will establish the feasibility (recruitment and retention) and acceptability (helpfulness, satisfaction, and impact) of the multicomponent LARKSPUR intervention in patients with FMS.

**5.1.1.2** To conduct a randomized pilot trial to estimate the effect size of the LARKSPUR intervention in FMS pain (primary outcome), as well PA, depressive symptoms, physical functioning, and stress appraisals (secondary outcomes) and explore racial/ethnic disparities. We hypothesize that intervention participants will report more frequent PA, decreased depressive symptoms, enhanced physical functioning, improved stress appraisals,

and reduced FMS pain (intensity and interference) immediately following the intervention (approximately 8 weeks), and at 1-Month Follow-Up.

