## **6 Study Methods**

### **6.1 General Study Design and Plan**

The trial is a randomized, longitudinal, parallel-group, attention-controlled trial. Treatment allocation is a 1:1 ratio. Participants are randomly assigned to LARKSPUR or an emotion-reporting-only attention control condition stratified by race/ethnicity; non-Hispanic Black, Hispanic, or non-Hispanic other (e.g., White, Asian) after completion of eligibility screening

and baseline assessments (see Table 1 for the schedule of trial events). All participants will know their intervention/attention control status.

The LARKSPUR study protocol states that one of the Primary Outcomes is to establish feasibility (Retention as Measured by Change in Enrollment), so Retention will be tested for superiority.

The LARKSPUR study protocol states that the secondary objectives include hypotheses that “intervention participants will report more frequent PA, decreased depressive symptoms, enhanced physical functioning, improved stress appraisals, and reduced FMS pain (intensity and interference) immediately following the intervention (approximately 8 weeks), and at 1-Month Follow-Up.” Therefore, all Secondary Endpoints will be tested for superiority.

Other Primary Outcomes characterize the treatment group only and are not tested statistically.

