**8.2    Covariates and Subgroups**

Baseline covariates for each secondary outcome are expected to correlate with their matching secondary outcome scores at Post-Intervention and 1-Month Follow-Up assessments. Therefore, analyses of each secondary outcome will include participant Baseline scores for adjustment of superiority analyses of treatment differences.

Race/ethnicity was used to stratify treatment allocation and will be adjusted for in primary analyses if sample sizes within each race/ethnicity—treatment subgroup is sufficient (i.e., greater than 5). Otherwise, race/ethnicity will be omitted from primary analyses.

Given the pilot nature of the study, sample size was chosen based on feasibility indicators (recruitment, retention, adherence) rather than on formal power calculations [see 1]. Accordingly, interaction analyses comparing treatment effects by race/ethnicity, age and gender are exploratory.

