## 10 Efficacy Analyses

All efficacy variables will be summarized by treatment group in accordance with Section 9.

Except for the two Daily Survey Measures [Change in Affective Reactivity to Stress as Measured by the Daily Modified Differential Emotions Scale (mDES) and Change in Affective Reactivity to Stress as Measured by the Daily Inventory of Stressful Events (DISE)], all Secondary Outcomes will be analyzed using mixed-effects analysis of variance with treatment group by time (Post-Intervention, 1-Month Follow-Up) adjusting for the mean-centered Baseline scores on the respective secondary outcome. Models will include fixed effects for treatment (LARKSPUR vs. control), time (Post-Intervention, 1-month Follow-Up), and the interaction between treatment and time. Random intercepts for participants will be included to account for within-participant correlation over time. The modified Intention-to-Treat sample described in Section 8.1 will be used. Treatment groups will be compared at Post-Intervention, at 1-Month Follow-Up, and with respect to their change from Post-Intervention to 1-Month Follow-Up using 2-sided tests at the 5% significance level under the null hypothesis of no difference in means/change. All assumptions for the mixed-effects models will be assessed by inspection of plots of within-participant and between-person residuals. Standard errors, degrees of freedom, 95% confidence intervals, and p-values will be adjusted using the Kenward-Roger method to control the significance level [4]. Restricted maximum likelihood (REML) estimation will be used. All analyses are exploratory with the aim of hypothesis generation as described in the Study Protocol given the pilot nature of this study.

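### Protocol 8 and SAP 4.2 state the Aim 2 analysis as a pre-post change, which contradicts the randomised effect-size objective and the between-arm analyses that the SAP already plans

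*SAP*

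**What the plan says.** The scope section of the SAP (4.2) states: "Aim 2 will be addressed using a pre-post design". It continues that, to judge how far LARKSPUR is likely to help, "a post-versus-pre-difference will be sought to estimate the change in" patients' outcomes, with pain self-management as the example. No comparison with control is mentioned. Protocol 8 carries essentially the same text, and it is the only Aim 2 analysis in the protocol.

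The objective is worded differently. SAP 5.1.1.2, matching Protocol 1.1.1, is "To conduct a randomized pilot trial to estimate the effect size of the LARKSPUR intervention in FMS pain (primary outcome", with positive affect, depressive symptoms, physical functioning and stress appraisals as secondary outcomes.

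The rest of the SAP follows the objective:

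- Section 6.1: "The trial is a randomized, longitudinal, parallel-group, attention-controlled trial. Treatment allocation is a 1:1 ratio". After citing the protocol's hypotheses for these outcomes, it concludes: "Therefore, all Secondary Endpoints will be tested for superiority".
- Section 8.2: "analyses of each secondary outcome will include participant Baseline scores for adjustment of superiority analyses of treatment differences".
- Section 10: "Models will include fixed effects for treatment (LARKSPUR vs. control", together with time and the treatment-by-time interaction. The groups are compared at Post-Intervention and at 1-Month Follow-Up.
- Section 10.2.1 applies the Section 10 model to the eight survey measures and gives the two daily measures their own treatment-by-time-by-day model.

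On the control condition, Protocol 3 reports from past research that "participants perceive it as being beneficial, providing some of the features of a placebo control".

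**The concern.** A post-minus-pre change and a randomised between-arm difference are different estimands. The first contains everything that moves patients between the two assessments: treatment, placebo response, regression to the mean, and the effect of daily self-monitoring. The second removes whatever the two arms share.

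The shared part is unlikely to be negligible here by design. Protocol 3 says that LARKSPUR participants also complete the daily emotion check-in that makes up the control condition, and it credits that condition with placebo-like features.

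The label Aim 2 is attached to an analysis only in Protocol 8 and SAP 4.2. Section 10 does not say that it answers Aim 2 and does not use the term effect size. A reader who looks up how the Aim 2 effect size is obtained is therefore led to the pre-post sentence. With both statements current, either figure could later be presented as prespecified.

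**Working it through.** **1. The passages side by side.** The documents give no numerical figure on this point to reproduce, so the check is first one of text.

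| Place | Contrast stated | Control arm |
|---|---|---|
| Protocol 8, Aim 2 | post minus pre | not mentioned |
| SAP 4.2, Aim 2 | post minus pre | not mentioned |
| Protocol 1.1.1; SAP 5.1.1.2 | effect size from a randomised pilot | required by the design |
| SAP 6.1 | superiority, all secondary endpoints | used |
| SAP 8.2 | treatment differences, adjusted for baseline score | used |
| SAP 10 (eight survey measures) | LARKSPUR vs control at each of two visits, 2-sided 5% | used |
| SAP 10.2.1 (two daily measures) | LARKSPUR vs control, with Baseline as a level of time, by day | used |

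All ten endpoints in SAP 5.2.2 have a named between-arm analysis. No model, test or contrast anywhere is specified for the LARKSPUR arm alone. Pain self-management is not among the ten endpoints.

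**2. What each contrast estimates.** Let δ be the true treatment effect and m the change shared by both arms, in SD units.

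- LARKSPUR post minus pre: δ + m.
- Control post minus pre: m.
- Difference between arms: (δ + m) − m = δ.

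The pre-post figure equals the treatment effect only if m = 0. The documents give no value for m.

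**3. Illustration: no true effect.** Assumptions: δ = 0, equal SDs at both visits, pre-post correlation r of 0.5 or 0.7, normal approximation, 2-sided 5%. The number per arm is 75 in Protocol 3 and 45 in SAP 7, so both are shown.

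- Within-arm SE = √(2(1 − r)/n).
- Baseline-adjusted between-arm SE = √(2(1 − r²)/n).
- Within-arm rejection rate = 1 − Φ(1.96 − m/SE) + Φ(−1.96 − m/SE).

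Example with n = 75, r = 0.5, m = 0.2: SE = √(1/75) = 0.115, m/SE = 1.73, rejection rate 41%.

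| n per arm | m | Pre-post test rejects (r = 0.5; 0.7) | Between-arm SE (r = 0.5; 0.7) |
|---|---|---|---|
| 75 | 0.2 | 41%; 61% | 0.141; 0.117 |
| 75 | 0.5 | 99%; >99% | 0.141; 0.117 |
| 45 | 0.2 | 27%; 41% | 0.183; 0.151 |
| 45 | 0.5 | 92%; 99% | 0.183; 0.151 |

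Under the same assumptions the between-arm contrast has no bias from m and rejects 5% of the time.

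**4. Illustration: a small true effect.** Assume δ = 0.2 and m = 0.2 to 0.4. The pre-post figure is 0.2 + 0.2 = 0.4 to 0.2 + 0.4 = 0.6, which is 2 to 3 times δ. Suppose such a figure were used to size a later trial at 80% power, 2-sided 5%, with a two-sample t-test. The numbers per arm would be:

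- d = 0.2: 394
- d = 0.4: 100
- d = 0.6: 45

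(The normal approximation 2(1.960 + 0.842)²/d² gives one fewer in each case.) True power at d = 0.2 would be Φ(0.2√(100/2) − 1.96) = Φ(−0.546), about 29%, with 100 per arm. With 45 per arm it would be about 16%.

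**The case against.** The strongest reply is that the SAP does assign the analysis. Section 6.1 goes from the Aim 2 hypotheses straight to superiority testing. Section 10.2.1 sends the eight survey measures to the Section 10 model and gives the two daily measures a between-group model. The SAP (version 1.0, February 2023) is also later and more detailed than the protocol (June 2021). This stands. A reader of SAP 4.2 might infer that Aim 2 will be answered without the control arm, but the documents do not support that.

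A second reply is that the pre-post wording may only describe when outcomes are measured inside a randomised comparison. That reading is possible, since the endpoints are phrased as changes and SAP 4.1 hypothesises greater improvements. But the sentence that follows names the post-minus-pre difference as the way to judge benefit, and nothing in either place adds a comparison with control.

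A third reply concerns consequences. A reader might infer that the effect size will be inflated two- or three-fold and the next trial undersized. The documents do not support that either. They give neither δ nor m. SAP 7 makes feasibility the primary purpose, SAP 10 calls all analyses exploratory, and no passage says that this estimate will size the later trial. The figures in steps 3 and 4 apply only if the between-arm models were set aside and the pre-post figure used instead.

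What survives is narrower. In the protocol the pre-post text stands alone, and the SAP repeats it in its own scope section as current text. No rule says which statement prevails. The protocol's text cannot deliver the effect size that the protocol sets as its objective.

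**Conclusion.** The point holds as an unreconciled and wrong statement of the Aim 2 estimand in Protocol 8 and SAP 4.2. It is not a flaw in the planned models: the between-arm comparison needed for Aim 2 is already specified for every secondary endpoint.

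The pre-post figure, if reported as the Aim 2 effect, would be off by the full change shared with control. The size of that change is unknown from the documents, so every inflation, rejection-rate and sample-size figure above is illustrative and rests on assumed values of m, δ and r. The direction is upward if the control arm also improves.

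The wording should be corrected, because the conflict leaves a choice of estimand open after results are known and costs almost nothing to remove.

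**What to change.** In SAP 4.2 and Protocol 8, replace the two pre-post sentences with a statement along these lines:

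*Aim 2 is estimated by the difference LARKSPUR minus control at Post-Intervention and at 1-Month Follow-Up, with 95% confidence intervals. The baseline-adjusted models of SAP Section 10 are used for the eight survey measures and the models of Section 10.2.1 for the two daily measures. Within-arm changes from baseline are reported as description only.*

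Replace the example of pain self-management with the PROMIS Pain Intensity and Pain Interference endpoints. If a standardised effect size is wanted, name the standardiser; which one is optional and does not affect this point.

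The cost is wording in two places, with the protocol change going through the usual amendment route. No new data, model or analysis is needed. The one downside for the sponsor is that the reported effect may be smaller than a within-arm change would have been.
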